### **7.3 SELECTION CRITERIA (LTE PERIOD)**

All the patients who will complete the 6-month-core period will be allowed to enter the LTE period, if sarilumab is not yet commercially available in France (as monotherapy or in combination with csDMARDs).

## 8 STUDY TREATMENTS

### 8.1 INVESTIGATIONAL MEDICINAL PRODUCT

The investigational medicinal product (IMP) is sarilumab (Kevzara®) that is expected to be available commercially in the second half of 2018 in France.

Sarilumab will be supplied by the Sponsor in 1.14 mL ready-to-use, single-use prefilled glass syringes delivering 200 mg (175 mg/mL) of sarilumab for subcutaneous (SC) injections. A patient will use one prefilled syringe for each dosing. In case of specific laboratory abnormalities over the treatment period (see section 10.4.6 for more details), the Sponsor will supply 1.14 mL ready-to-use, single-use prefilled glass syringes delivering 150 mg (131.6 mg/mL) of sarilumab for SC injections, using the Interactive Voice Response System (IVRS).

During the treatment period, the IMP should be administered every 14 days; however an IMP administration window of  $\pm 3$  days is permitted per protocol to accommodate exceptional circumstances, eg, laboratory test result pending), ongoing adverse event, or patient scheduling difficulty.

Patients and/or their non-professional caregivers will be trained to administer IMP at the start of the treatment period. This training must be documented in the patients' study file. The study coordinator or designee may administer the first injection, or allows the patient to self-inject, under observation, and provide feedback on technique, thus combining the initial dose administration as part of the training procedure on Treatment Period Day 1 (Visit 2). If SC injections have to be done on days when the patient has a study visit, the IMP will be administered following clinic procedures and blood collection. For doses not given at the study site, a diary card will be provided to record information pertaining to these injections; these diaries will be kept as source data in the patients' study file.

If a patient or non-professional caregiver is completely unable to administer sarilumab at home, it is permitted that the dose will be administered as described above by a home nurse as scheduled.

Sarilumab is administered as subcutaneous injection in the abdomen (except for the 2-inch area surrounding the navel), the front of the thigh or in upper arm. The site for each injection should be rotated. Injections should not be administered into skin that is sore (tender), bruised, red, hard, scarred or damaged. The injection sites will be inspected by the site personnel at each visit and any injection site reactions (ISRs) should be documented appropriately on the AE electronic Case Report Form (eCRF) page.

### 8.2 NON-INVESTIGATIONAL MEDICINAL PRODUCT(S)

Not applicable.

### **8.3 BLINDING PROCEDURES**

Not applicable.

### **8.4 METHOD OF ASSIGNING PATIENTS TO TREATMENT GROUP**

Not applicable.

### **8.5 INVESTIGATIONAL MEDICINAL PRODUCT PACKAGING AND LABELING**

Packaging is in accordance with the administration schedule. The content of the labeling is in accordance with the local regulatory specifications and requirements. In particular, study drug packaging will be overseen by the Sponsor clinical trial supplies department and bear a label with the identification required by local law, the protocol number, drug identification and dosage.

The primary treatment supply shall contain two kits of one prefilled syringe per patient in each, the first for the IMP injection at the inclusion visit and the second for the second injection to be done at home. Following kits of one prefilled syringe will be provided for each patient, using the IVRS.

Additional treatment kits to provide medication under circumstances as damaged kit or unusable kit will be allocated by IVRS.

### **8.6 STORAGE CONDITIONS AND SHELF LIFE**

Investigators or other authorized persons (eg, pharmacists) are responsible for storing the IMP in a secure and safe place in accordance with local regulations, labeling specifications, policies, and procedures.

Control of IMP storage conditions, especially control of temperature (eg, refrigerated storage) and information on in-use stability and instructions for handling the Sanofi compound must be managed according to the rules provided by the Sponsor.

All sarilumab PFS must be stored at a controlled temperature of 2-8°C (with no freezing), and in the original carton in order to protect from light. After removing the PFS from the refrigerator, it should be allowed to warm up at room temperature before injecting sarilumab (for at least 30 minutes before using), and it should be administered within 14 days and should not be stored above 25°C.

## 8.7 RESPONSIBILITIES

The Investigator, the hospital pharmacist, or other personnel allowed to store and dispense the IMP will be responsible for ensuring that the IMP used in the clinical trial is securely maintained as specified by the Sponsor and in accordance with applicable regulatory requirements.

All IMP will be dispensed in accordance with the Investigator's prescription and it is the Investigator's responsibility to ensure that an accurate record of IMP issued and returned is maintained.

Any quality issue noticed with the receipt or use of an IMP (deficiency in condition, appearance, pertaining documentation, labeling, expiration date, etc.) must be promptly notified to the Sponsor. Some deficiencies may be recorded through a complaint procedure.

A potential defect in the quality of IMP may be subject to initiation of a recall procedure by the Sponsor. In this case, the Investigator will be responsible for promptly addressing any request made by the Sponsor, in order to recall the IMP and eliminate potential hazards.

Under no circumstances will the Investigator supply IMP to a third party (except for patients enrolled in the study), allow the IMP to be used other than as directed by this clinical trial protocol, or dispose of IMP in any other manner.

### 8.7.1 Treatment accountability and compliance

Measures taken to ensure and document treatment compliance and IMP accountability include:

- Proper recording of treatment kit number or packaging number as required on appropriate electronic case report form (e-CRF) page for accounting purposes.
- A diary card will be provided to patients to record home injections. Patients will be asked to return all empty drug supply boxes, unused PFS, and diary cards to the clinic at each visit as a measure of drug accountability and patient compliance. Sharps containers for any used PFS will be provided locally to patients for home usage. After home injections, the used syringes must be placed into the sharps containers immediately. The sharps containers should be returned to sites and discarded by the site staff at the frequency per local schedule. So, sharps containers for used syringes, back-pack and insulated cooling bag for transport from sites to patient's home will be provided by the sponsor to the site for the patients.
- The study coordinator tracks treatment accountability/compliance, either by diary, or by counting the number of unused/used treatment kits and fills in the appropriate page of the patient treatment log. The monitor in charge of the study then checks the data entered on the IMP administration page by comparing them with the IMP that has been retrieved and the patient treatment log form.

### 8.7.2 Return and/or destruction of treatments

All partially used or unused treatments will be retrieved by the Sponsor or destroyed at study site.

A detailed treatment log of the returned/destroyed IMP will be established with the Investigator (or the pharmacist) and countersigned by the Investigator and the monitoring team. The Investigator will not destroy the unused IMP unless the Sponsor provides written authorization. In this case, written documentation of destruction must contain the following:

- Identity (kit or packaging numbers and subject numbers) of IMP destroyed
- Quantity of IMP destroyed
- Date of destruction
- Method of destruction
- Name and signature of responsible person who destroyed IMP.

In case of PFS failure, or if there are any issues with the drug, the syringe should not be destroyed, and instead should be returned to the appropriate Sponsor clinical trial supplies department for further assessment.

## 8.8 CONCOMITANT MEDICATION

A concomitant medication is any treatment received by the patient concomitantly to any IMP(s). Concomitant therapy includes any medication (e.g., prescription drugs, over-the-counter drugs, herbal/homeopathic remedies, nutritional supplements) used by a patient from 7 days prior to Screening to the study completion/early termination visit. All concomitant medications should be reported to the Investigator and recorded on the corresponding pages of the patient e-CRF, along with a description of the type of drug or procedure, the amount, duration, reason for administration of drug, and the outcome of any procedure.

### 8.8.1 Prohibited medications

The use of any **biologic DMARDs**, including but not limited to etanercept, infliximab, anakinra, rituximab, abatacept, tocilizumab, certolizumab, golimumab, adalimumab and any **targeted synthetic DMARDs** such as tofacitinib, as well as any biologic DMARDs or JAK inhibitors approved during the study are not permitted throughout the study treatment and until 4 weeks following the End-of-Treatment visit. If any of these treatments are used, the patient should be discontinued but the patient will continue to be followed up for safety for at least 4 additional weeks.

The use of **intramuscular (IM), IV and more than one intra-articular glucocorticoid injection** is not permitted throughout the study treatment and until 4 weeks following the End-of-Treatment visit. In cases where IM, IV, or more than intra-articular corticosteroids are needed, patient's withdrawal should be considered.

Immunization with a **live or attenuated vaccine** is prohibited within 4 weeks prior to Baseline, for the duration of study participation and 12 weeks after administration of the last dose of IMP.

Treatment with **any investigational medicinal product** other than sarilumab is not permitted.

### 8.8.2 Permitted medications

**DMARDs:** Treatment with csDMARDs (azathioprine, chloroquine, hydroxychloroquine, leflunomide, MTX, sulfasalazine), at a stable dose initiated at least 4 weeks prior to Baseline, is permitted during the study. If applicable, DMARDs can be used alone or in combination except for the combination of MTX and leflunomide. If applicable, patients should remain on the same background csDMARD(s) throughout the study.

The dose and route of administration of csDMARDs at entry in the study should be continued without change during the study period unless an adjustment is necessary for safety reasons. All biologic DMARDs are prohibited during the study and must be discontinued and washed out prior to the initiation of study treatment. The use of prohibited medications will require the patients to be withdrawn from the study.

**Folic Acid:** In order to minimize MTX toxicity, all patients treated with MTX will receive folic acid or equivalent at a dose of at least 5 mg/week. This can either be given as a single weekly dose usually 48 hours after MTX administration or be divided into daily doses to achieve at least 5 mg folic acid per week. It is the Investigator's decision as to which dosing regimen is used.

**Oral corticosteroids:** Patients may receive oral corticosteroids at dose of  $\leq 15$  mg/day prednisone or equivalent during the study, if initiated at least 4 weeks prior to Baseline. To treat AE for a condition not related to RA that requires a corticosteroid dose modification, increased doses of oral corticosteroids during the study will be permitted.

Corticosteroids can be stepwise discontinued at the investigator's discretion in eligible patients in order to achieve a steroid-free condition. After a potential increased dose of oral corticosteroids, up to 15 mg of prednisone daily (or equivalent), the corticosteroid dose should be tapered down to the previous level as rapidly as medically possible. In cases where increased corticosteroids doses for RA conditions can't be tapered down during the study, patient maintenance in the study should be reevaluated based on the investigator's judgment.

Intranasal, inhaled, or topical corticosteroids as per label are permitted, as needed throughout the course of the study.

**NSAIDs:** Patients may be treated with NSAIDs or cyclo-oxygenase-2 inhibitors (COX-2) at a stable dose that was initiated at least 4 weeks prior to Baseline, up to the maximum recommended dose during the study. The dose should remain stable during the study, unless dose reduction is required for safety reasons. The choice and doses of NSAIDs and COX-2 are at the discretion of the Investigator. The addition of new NSAIDs during the study treatment period is not permitted.

**Analgesics (other than NSAIDs) and opioids:** Analgesics and opioids up to the maximum recommended doses may be used for pain as required. However, patients should not take analgesics or opioids within 12 hours prior to a visit where clinical efficacy assessments are performed.

**Lipid-lowering agents:** Lipid lowering drugs are permitted. Dose should be stable for at least 6 weeks prior to screening. Anti-IL-6 drugs, including sarilumab, are known to increase serum

cholesterol levels and this effect will be closely monitored during the study. Use of lipid-lowering agents in patients with elevated lipids at any time during the study are strongly encouraged in conjunction with the treating physician's clinical judgment and guidelines such as National Cholesterol Education Program Adult Treatment Panel III (NCEP ATP III, see Appendix C).

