## **10.3 HANDLING OF PATIENT TEMPORARY OR PERMANENT TREATMENT DISCONTINUATION AND OF PATIENT STUDY DISCONTINUATION**

The IMP should be continued whenever possible. In case the IMP is stopped, it should be determined whether the stop can be made temporarily; permanent IMP discontinuation should be a last resort. Any IMP discontinuation must be fully documented in the eCRF. In any case, the patient should remain in the study as long as possible.

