### **10.3.3 List of criteria for permanent treatment discontinuation**

The patients may withdraw from treatment with the IMP if they decide to do so, at any time and irrespective of the reason, or this may be the Investigator's decision. All efforts should be made to document the reason(s) for treatment discontinuation and this should be documented in the eCRF.

Patients must discontinue sarilumab if they experience any of the following:

- Pregnancy in female patients
- Opportunistic infections (including but not limited to tuberculosis and disseminated herpes zoster) and serious infections
- Gastro-intestinal perforations or diverticulitis
- Neutropenia (ANC <500 cells/mm^3)
- Thrombocytopenia (platelet count <50,000 cells/mm^3)
- ALT or AST elevation of >5 times ULN
- Malignancies (with the exception of local basal or squamous cell carcinoma of the skin or carcinoma in situ of the cervix uteri that have been excised and cured)
- Signs/symptoms of anaphylaxis or hypersensitivity following SC administration of sarilumab
- Use of biologic DMARD other than sarilumab
- Any AEs, per Investigator's judgment, that may jeopardize the patient's safety.

Any abnormal laboratory value will be immediately rechecked for confirmation before deciding of permanent discontinuation of IMP treatment.

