### **10.3.4 Handling of patients after permanent treatment discontinuation**

Patients will be followed-up according to the study procedures specified in this protocol up to the scheduled date of study completion, or up to recovery or stabilization of any AE to be followed-up as specified in this protocol, whichever comes last.

If possible, and after the permanent discontinuation of treatment, the patients will be assessed using the procedure normally planned for the last dosing day with the IMP (see Section 1.2).

All cases of permanent treatment discontinuation must be recorded by the Investigator in the appropriate pages of the eCRF when considered as confirmed.

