### **10.3.5 Procedure and consequence for patient withdrawal from study**

The patients may withdraw from the study before study completion if they decide to do so, at any time and irrespective of the reason without any effect on their care. However, if patients no longer wish to take the IMP, they will be encouraged to remain in the study.

The Investigators should discuss with them key visits to attend. The value of all their study data collected during their continued involvement will be emphasized as important to the public health value of the study.

Patients who withdraw from the study treatment should be explicitly asked about the contribution of possible AEs to their decision, and any AE information elicited must be documented.

All study withdrawals must be recorded by the Investigator in the appropriate screens of the eCRF and in the patient's medical records. In the medical record, at least the date of the withdrawal and the reason should be documented.

In addition, a patient may withdraw his/her consent to stop participating in the study. Withdrawal of consent for treatment should be distinguished from withdrawal of consent for follow-up visits and from withdrawal of consent for non-patient contact follow-up, eg, medical record checks. The site should document any case of withdrawal of consent.

For patients who fail to return to the site, unless the patient withdraws consent for follow-up, the Investigator must make the best effort to re-contact the patient (eg, contact patient's family or private physician, review available registries or health care databases), and to determine his/her health status, including at least his/her vital status. Attempts to contact such patients must be documented in the patient's records (eg, times and dates of attempted telephone contact, receipt for sending a registered letter).

Patients who have withdrawn from the study cannot be retreated in the study. Their inclusion and treatment numbers must not be reused.

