#### **10.4.3 General guidelines for reporting adverse events**

- All AEs, regardless of seriousness or relationship to IMP, spanning from the signature of the informed consent form until the end of the study as defined by the protocol for that patient, are to be recorded on the corresponding page(s) or screen(s) of the eCRF.

- Whenever possible, diagnosis or single syndrome should be reported instead of symptoms. The Investigator should specify the date of onset, intensity, action taken with respect to IMP, corrective treatment/therapy given, additional investigations performed, outcome, and his/her opinion as to whether there is a reasonable possibility that the AE was caused by the IMP or by the study procedure(s).
- The Investigator should take appropriate measures to follow all AEs until clinical recovery is complete and laboratory results have returned to normal, or until progression has been stabilized, or until death, in order to ensure the safety of the patients. This may imply that observations will continue beyond the last planned visit per protocol, and that additional investigations may be requested by the monitoring team up to as noticed by the Sponsor.
- When treatment is prematurely discontinued, the patient's observations will continue until the end of the study as defined by the protocol for that patient.
- Laboratory, vital signs or ECG abnormalities are to be recorded as AEs only if:
  - Symptomatic and/or
  - Requiring either corrective treatment or consultation, and/or
  - Leading to IMP discontinuation or modification of dosing, and/or
  - Fulfilling a seriousness criterion, and/or
  - Defined as an AESI.

Instructions for AE reporting are summarized in Table 1.

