#### **11.4.2 Analyses of efficacy endpoints**

##### **11.4.2.1 Analysis of primary efficacy endpoint**

The primary study objective is to assess the change in RAID score from baseline to W24. The number of available data, mean, standard deviation, median and range (minimum, maximum) will be provided with the 95% confidence interval of mean change from baseline to W24. Main analysis will be done on ITT population. Sensitivity analysis will be conducted in reproducing the same analysis using the per-protocol population.

In addition, multivariate analyses such as ANCOVA (Analyze of Covariance), Logistic Regression and Multiple Correspondences analysis can be performed from baseline in order to exploratory explain different profiles of patients. The details of these analyses will be described on the statistical analyses plan before database frozen.

In case of any event mentioned below, the last available endpoint before the considered event will be taken in account (for RAID score for primary endpoint and for all other secondary endpoints):

- Lack of efficacy
  - More than one glucocorticoid infiltration per articulation
  - Dose increase of an ongoing glucocorticoid or start of systemic glucocorticoid treatment
  - Change in NSAID due to lack of efficacy or adverse event considered as related to treatment by the investigator
- Missing data
  - Treatment discontinuation due to lack of efficacy or adverse event (except for AEs due to NSAID). For all other cases, missing data will not be replaced.

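### When a patient starts another biologic DMARD, Protocol 8.8.2 requires withdrawal from the study while 10.3.3–10.3.4 require continued follow-up, and nothing says which prevails

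*Protocol*

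**What the plan says.** Four parts of the protocol bear on a patient who starts another biologic DMARD during treatment.

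- **8.8.1 Prohibited medications** bans biologic and targeted synthetic DMARDs during treatment and for 4 weeks after the End-of-Treatment visit. If one is used, "the patient should be discontinued but the patient will continue to be followed up for safety for at least 4 additional weeks". It does not say whether the patient is discontinued from sarilumab or from the study.
- **8.8.2 Permitted medications** repeats that all biologic DMARDs are prohibited and adds: "The use of prohibited medications will require the patients to be withdrawn from the study".
- **10.3.3** lists events after which sarilumab must be stopped for good. One is "Use of biologic DMARD other than sarilumab". Targeted synthetic DMARDs are not on the list.
- **10.3.4** covers what follows a permanent stop: "Patients will be followed-up according to the study procedures specified in this protocol up to the scheduled date of study completion", or until any adverse event has resolved or stabilised, whichever is later.

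The surrounding text leans towards continued follow-up. Section 10.3 says "In any case, the patient should remain in the study as long as possible". Section 10.3.5 separates stopping the drug from leaving the study: "if patients no longer wish to take the IMP, they will be encouraged to remain in the study". Section 10.4.3 says that after a premature stop "observations will continue until the end of the study as defined by the protocol for that patient".

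On the analysis side, Protocol 11.4.2.1 takes the last RAID before certain events. Its lack-of-efficacy list consists of glucocorticoid and NSAID changes, for example "Dose increase of an ongoing glucocorticoid or start of systemic glucocorticoid treatment". A separate entry, under missing data, covers stopping treatment for lack of efficacy or an adverse event. SAP 6.4 restates the rule for such stops, with lack of efficacy defined by reference to Protocol 11.4.2.1. Starting another DMARD is named in neither place.

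**The concern.** Adding or switching to another biologic is a foreseeable event in patients who have already failed or not tolerated earlier treatment. It is also the event after which it matters most whether later data are collected and what they mean. If one site withdraws the patient and another keeps following, two patients with the same history get different safety observation. One has a Week 24 RAID and the other does not. Where the value is collected, it may describe the new drug rather than sarilumab, and the analysis rules do not say directly how to treat it.

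**Working it through.** The conflict involves no figure, so the check sets the texts side by side.

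**Step 1: which pairs conflict.**

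| Pair | Can both be obeyed? | Reason |
|---|---|---|
| 8.8.2 and 10.3.4 | No | Out of the study, against study procedures to the scheduled end |
| 8.8.2 and 10.3.3 | Yes | A withdrawn patient also stops sarilumab |
| 8.8.1 and 10.3.4 | Yes | The 4 weeks are a minimum, so longer follow-up satisfies both |
| 8.8.1 and 8.8.2 | Yes | The 4 weeks can be safety follow-up after withdrawal |

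One pair fails. It could be rescued by reading withdrawal from the study in 8.8.2 as withdrawal from study treatment. The sentence does not say that, and 10.3.5 uses the two ideas as distinct.

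**Step 2: what each reading produces.**

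- *8.8.2.* The patient has an early withdrawal visit, which includes RAID (Protocol 10.1.5). Protocol 6.1 also gives each patient a post-treatment visit 2 to 4 weeks after the last dose; the tasks listed in 10.1.6 do not include RAID. Section 8.8.1 adds its safety minimum. Under SAP 6.6, the withdrawal RAID can stand as Week 24 only if it falls on days 161 to 175.
- *10.3.4.* The scheduled visits continue, so a Week 24 RAID is collected, possibly on the new drug.

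For the length of safety follow-up only, take a switch at Week 12 (day 84) as an example. The 8.8.1 minimum is met on day 84 + 28 = 112. Week 24 is day 168, which is 168 − 112 = 56 days later. This says nothing about RAID, because the 8.8.1 follow-up is for safety.

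**Step 3: what the analysis rules do with the patient.**

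| Why sarilumab stopped | Last-value rule applies? |
|---|---|
| Adverse event | Yes, under Protocol 11.4.2.1 and SAP 6.4 (adverse events due to NSAIDs excepted) |
| Lack of efficacy | Yes on the face of Protocol 11.4.2.1; some doubt from the SAP 6.4 cross-reference, which can be read as pointing to the glucocorticoid and NSAID list |
| Other or unclear reason | No; missing values are not replaced |

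A second question cuts across the rows. Treatment discontinuation stands under missing data in both documents. Neither says whether the last value replaces a Week 24 RAID that was observed after the switch, as 10.3.4 would allow.

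The analysis question is also slightly wider than the conflict. The 8.8.1 ban ends 4 weeks after the End-of-Treatment visit. A patient who stopped sarilumab for some other reason and stayed under 10.3.4 could therefore start a biologic before Week 24 without breaching the protocol.

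**The case against.** The best defence is that 8.8.2 is a specific rule for prohibited drugs and 10.3.4 a general one, so a site could treat the first as an exception to the second. The supporting texts are also softer than they look. Section 10.3 asks only for as long as possible, the encouragement in 10.3.5 concerns patients who choose to stop, and 10.4.3 leaves the end of study to be defined per patient. All of that is fair. But 10.3.3 names this very event and leads directly into 10.3.4, so both routes are specific to it, and the protocol gives no order of precedence.

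The analysis is also less exposed than it may appear. The mixed model in SAP 5.3.2.2 uses changes at earlier visits, so a patient without a Week 24 RAID can still contribute. The per-protocol sensitivity analysis may exclude these patients if the data review classes the switch as a major deviation, although the SAP does not list the deviations. Both points stand and limit the consequence.

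A reader might go further in three ways that the documents do not support:

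- *That there are three mutually incompatible instructions.* The 8.8.1 follow-up period is a minimum and fits either route.
- *That a withdrawn patient is seen only at the early withdrawal visit.* The post-treatment visit and the 8.8.1 safety period also apply.
- *That a switch for lack of efficacy has no analysis rule.* Protocol 11.4.2.1 has a separate entry for it.

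**Conclusion.** The conflict between 8.8.2 and 10.3.3–10.3.4 is real. It affects the length of safety follow-up and whether a Week 24 RAID is collected. The ambiguity in 8.8.1 and the omission of targeted synthetic DMARDs from 10.3.3 are lesser wording faults on the same subject. The remaining analysis gap is narrow: switches for reasons other than an adverse event or lack of efficacy, and the status of a Week 24 RAID observed after any switch.

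The effect on the primary mean cannot be calculated. The documents give neither an expected number of such patients nor their likely RAID on another drug. It is probably small, on the assumption that few patients switch before Week 24, and its direction is uncertain. A reader might infer that the primary result is materially biased; nothing in the documents shows that. This is a minor but worthwhile correction. The conclusion rests on reading withdrawal from the study literally, as 10.3.5 supports.

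**What to change.** 1. **Protocol 8.8.2:** replace the withdrawal sentence with: *A patient who starts another biologic or a targeted synthetic DMARD is permanently discontinued from sarilumab (10.3.3) and followed per 10.3.4.* The present sentence covers every prohibited treatment, so the amendment should also say what happens with the others that have no consequence of their own in 8.8.1, such as live vaccines.
2. **Protocol 8.8.1:** state that discontinuation means from sarilumab, with follow-up per 10.3.4.
3. **Protocol 10.3.3:** add targeted synthetic DMARDs to the list.
4. **Protocol 11.4.2.1 and SAP 6.4:** add the start of another biologic or targeted synthetic DMARD, for any reason, to the events after which the last earlier RAID is used, as for glucocorticoid changes. State that RAID values after the switch are not counted as sarilumab Week 24 values, even when observed.

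Making 10.3.4 give way to 8.8.2 would also remove the contradiction. Keeping 10.3.4 is preferable because it preserves safety data and fits sections 10.3 and 10.3.5.

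The cost is a short protocol amendment, which needs ethics committee approval before use (Protocol 15), and one SAP line. No visits are added to the schedule. If patient follow-up is already complete, only the SAP line can still have an effect. It would remain useful, since sites may have followed different sections.
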